Percutaneous Peripheral Neuromodulation for Postoperative Analgesia

NCT: NCT0289810

Date: 05/17/2018

Written, informed consent will be obtained using an IRB-approved ICF prior to any study procedures. Lead insertion may occur up to 2 weeks prior to surgery within the CTRI or orthopedic clinic, or the morning of surgery in the CTRI or regional anesthesia induction area (it just depends on subject and surgeon preference, as well as logistical issues such as the time of the surgery and availability of the investigators). Baseline muscle strength will be measured with a pressure transducer.

Preoperative lead insertion (approximately 1-3 hours). A percutaneous, helically-coiled, insulated electrical lead will be inserted via an introducer needle at least 2 cm proximal or distal to the perineural catheter site along the target nerve using real-time ultrasound guidance:

Surgical Procedure Location	Perineural Catheter Location	Electrical Lead Location
Shoulder	Interscalene	Interscalene, supraclavicular, or suprascapular
At or distal to the elbow	Infraclavicular	Interscalene, supraclavicular or terminal nerve(s)
Foot or ankle	Popliteal-sciatic [adductor canal optional]	Subgluteal-sciatic [femoral optional]
Knee or distal thigh	Adductor canal [popliteal-sciatic optional]	Femoral [subgluteal-sciatic optional]

It will be optional for a conducting probe to be used prior to lead insertion—this allows identification of the optimal lead tip location relative to the target nerve by passing electrical current via the insulated probe. The desired end point is a pleasant paresthesia in the distribution of the target nerve reported by the subject. If used, the probe will be completely withdrawn following target location identification, and a lead subsequently inserted to the target location. Following needle removal, the percutaneous helical lead will have electric current passed using the SPRINT (SPR Therapeutics, Cleveland, OH) pulse generator to ensure accurate placement (a pleasant paresthesia in the distribution of the target nerve). It will be replaced, if necessary. The pulse generator will then be removed and the lead affixed to the skin using an occlusive dressing.

With the subject's permission we may photograph or videotape the procedures described above for educational, training, or publication purposes. The photos or video will focus only on the lead insertion site and affected limb. Ultrasound images from the procedure may also be collected. Every effort will be made to protect the subject's privacy and the photos or video will not include the subject's face or any other personal identifiers such as birthmarks. Subjects and their caretakers will be trained in device care and management, and given written instructions as well. Following successful lead insertion, a perineural catheter may be inserted, if the patient desires a catheter (with normal saline injection and not local anesthetic via the inserting needle). This will be used to deliver perineural local anesthetic as a rescue analgesic method postoperatively in case the SPRINT system provides inadequate analgesia.

Randomization. Within the recovery room, the surgeon often performs a standard neurologic examination (variable depending on the surgeon and surgical procedure), after which time the subject will have baseline end points measured, including a pain score at the surgical site using the Numeric Rating Scale (NRS, 0-10), pain score (NRS) within the target nerve distribution, and

sensory deficits (measured with alcohol pads and von Frey filament, compared to the contralateral limb within the cutaneous distribution of the target nerve). For their first pulse generator—“Stimulator A”—subjects will be randomized to one of two treatments—current or sham—using computer generated lists and opaque, sealed envelopes. The stimulator will then be attached to the lead and switched “on” (sham stimulator produces no current). The end points will be measured per the table below. Subsequently, the stimulator will be replaced by the alternative (current or sham)—“Stimulator B”. The subject will have the end points measured and the stimulator replaced with a unit set to deliver active current for the remainder of study participation (“Stimulator C”). Operating and recovery room pharmacologic analgesic requirements will be recorded. Of note, if a lead fails to provide paresthesias within the target nerve distribution with either Stimulator A or B (adjustment of stimulator settings allowed), the lead may be replaced at the discretion of the subject and investigators.

Of note, the data derived from the chronic pain literature suggests that there is a “carry over” effect following stimulation: analgesia is provided even after the cessation of electrical current. It remains unknown if this is true following surgery in the acute postoperative pain period. For subjects randomized to active current from Stimulator A, the data collected for Stimulator B placebo treatment may be lowered due to the carry over effect. Therefore, this data will not be compared with the baseline or Stimulator A outcome measures. However, it is valuable data to possibly detect and quantify the carry-over effect of the initial stimulation.

At any time, subjects may choose to have their perineural catheter bolused with local anesthetic and a perineural local anesthetic infusion begun (if they desired a catheter with subsequent insertion). Therefore, subjects will not risk receiving inferior analgesia by participating in this study. However, subjects also have the option of leaving their infusion pump off and using neuromodulation as their primary analgesic if the latter proves adequate—the decision is completely each subject’s and may be made any time prior to perineural catheter removal.

Subjects and their caretakers will be trained in device care and management, and given written instructions as well. Pain scores (resting and dynamic worst and average) will be collected daily for two weeks, along with oral analgesic requirements, perineural local anesthetic use, and sensory/motor deficits (all specific to the previous 24 hours). Perineural catheters will be removed at home upon subject request, after 3 days, or upon local anesthetic reservoir exhaustion, whichever comes first (standard-of-care). The electrical leads will be removed upon subject request, or after 30 days, whichever comes first. The leads will be removed at home by subjects or their caretakers (standard-of-care for perineural catheter withdrawal) or by investigators, depending on both investigator and subject preference. If removed by subjects or their caretakers, a picture of the extracted lead tip must be texted/mailed to investigators, or the physical lead returned to investigators for inspection. Subjects will be contacted no less than every 5 days following the initial 2-week period until their lead is removed; and, will then be contacted 1 and 3 months postoperatively and the end points again verbally collected.

Sample Size Estimation and Statistical Analysis Plan. This is a feasibility study to demonstrate proof-of-concept and generate data to help design and power subsequent definitive, randomized, controlled clinical trials. Therefore, a convenience sample of 40 subjects will be enrolled (10 additional subjects permitted to account for any drop-outs for a total of 50 subjects). Although this is a feasibility—and not definitive—investigation, we will treat as the primary end point the difference between the baseline pain score and pain score 5 minutes after the active (non-sham) electrical stimulator is first turned on.

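### The primary baseline pain score is read after an irregular surgeon's examination and before the remaining steps to switch-on, so any drift in pain in that gap may be counted as stimulator effect

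*Combined protocol and SAP*

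**What the plan says.** The Randomization paragraph of the combined protocol and SAP sets the recovery-room order. First, "the surgeon often performs a standard neurologic examination (variable depending on the surgeon and surgical procedure), after which time the subject will have baseline" measures taken. These include "a pain score at the surgical site using the Numeric Rating Scale (NRS, 0-10), pain score (NRS) within the target nerve distribution", followed in the list by "sensory deficits (measured with alcohol pads and von Frey filament, compared to the contralateral limb within the cutaneous distribution of the target nerve". For Stimulator A, "subjects will be randomized to one of two treatments", current or sham. Only then: "The stimulator will then be attached to the lead and switched" on. After the Stimulator A measurements, "Subsequently, the stimulator will be replaced by the alternative (current or sham", so subjects given sham first meet active current only as Stimulator B.

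The Sample Size Estimation and Statistical Analysis Plan paragraph defines the primary end point as "the difference between the baseline pain score and pain score 5 minutes after the active (non-sham) electrical stimulator is first turned on". It does not subtract a sham response, say which of the two baseline pain scores is meant, or name a test, alpha or SD. It calls the study a feasibility study whose data should help to power later trials.

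The supplied text states no interval between examination and baseline, and no record of whether the examination was done. The measurement table to which the Randomization paragraph refers is not in the supplied text.

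**The concern.** The baseline is one of the two numbers that make up the primary end point. Its timing is tied to an event that happens in some subjects and not others, and whose content depends on the surgeon and the operation. Several steps then separate the reading from the start of current.

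If pain is moving during that gap, the score subtracted is not the score at switch-on. A fall before any current flows would look like benefit, and a rise would hide benefit. One possible source of a fall is an examination that briefly raises pain which then settles.

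Because the primary change has no sham comparator, nothing in its definition removes such drift. The estimate is meant to inform the design of definitive trials, so a shifted mean change could carry into their effect-size assumptions.

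**Working it through.** **Order of events, from the Randomization paragraph**

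1. Surgeon's examination: not in every subject, content variable.
2. Baseline: surgical-site NRS, target-nerve NRS, then sensory testing as listed.
3. Randomization.
4. Stimulator A attached and switched on (active or sham).
5. Stimulator B, the alternative treatment.

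**What enters the primary change.** Write the primary change as baseline minus the score at 5 minutes of active current. It splits into two parts:

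(baseline − score at active switch-on) + (score at active switch-on − score at 5 minutes)

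The first part is drift without active current. For subjects given active current first, it covers sensory testing, randomization and attachment. For subjects given sham first, if baseline means the pre-randomization score, it also covers the whole sham period. The second part contains the stimulator response plus any drift during those 5 minutes.

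**The plan's own figure.** The only numerical statement is enrolment: 40 + 10 = 50, which reproduces. The 40 is a convenience sample, so there is no power calculation to check.

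**Illustration of size.** Every input except n = 40 is assumed, including the test. Let f be the share of subjects examined and s the rise in baseline that has settled by the 5-minute reading. The mean bias is f × s.

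- f = 0.5, s = 0.5: bias 0.25
- f = 0.5, s = 1: bias 0.50
- f = 0.8, s = 1: bias 0.80

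With an SD of change of 2, SE = 2/√40 = 0.316, so these biases equal 0.79, 1.58 and 2.53 SE. The chance of a two-sided one-sample t test giving p<0.05 when the stimulator does nothing (noncentral t, 39 df, noncentrality = bias/SE) is:

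| Bias (NRS points) | SD 1.5 | SD 2 | SD 2.5 |
|---|---|---|---|
| 0 | 5% | 5% | 5% |
| 0.25 | 18% | 12% | 10% |
| 0.50 | 54% | 34% | 24% |
| 0.80 | 91% | 69% | 51% |

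**Added noise.** A 1-point artefact in half of subjects has variance 0.5 × 0.5 × 1² = 0.25. If it is independent of other variation, an SD of 2 becomes √(4 + 0.25) = 2.06. Noise is therefore a minor issue; the shift in the mean is the one that matters.

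**The case against.** The case against is substantial, and most of it stands.

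- **Provoked pain.** A reader might infer that the examination hurts and that this pain is counted as stimulator effect. Nothing in the documents says that it provokes pain. If it does not, this source of bias is zero.
- **Interval.** A reader might take the baseline to follow immediately after the examination. The text gives order, not interval. That order at least keeps the examination from falling between baseline and the 5-minute score.
- **Number of readings.** A reader might conclude that there is only a single baseline reading. Two pain scores are named, and the schedule table is missing from the supplied text. A repeat or time-zero reading may be in that table.
- **Sensory testing.** It is listed after the pain scores. Done in that order it cannot raise them. If it provoked pain, it would raise later scores and work against the stimulator.
- **Randomization.** It follows baseline, so examination effects should balance between the groups, and an active-versus-sham comparison in the Stimulator A period is protected. Sham-first subjects also show how pain moves without current.
- **False-positive rates.** They need a test and an alpha that the plan does not specify, and this is a feasibility study.

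What the objections do not remove is the definition of the primary end point. It is a within-subject change, not the randomized contrast, so the protection from randomization does not reach it.

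**Conclusion.** The concern holds in a limited form. The primary end point subtracts a score taken after an irregular examination at an unstated interval, and before the remaining steps to switch-on. Because the change is not set against sham, drift in that gap may be counted as stimulator effect.

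The documents give neither the size nor the direction of any drift. On the assumed inputs it would matter at about 0.5 to 1 point of settling and would be slight at a mean bias of 0.25. The percentages show sensitivity and are not estimates for this trial. The conclusion also assumes that the missing schedule table contains no reading at switch-on that serves as the primary baseline.

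This is one component of a wider weakness, an uncontrolled pre-post primary end point. The change below is worth considering as a cheap improvement; it is not a condition for the study to be interpretable.

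**What to change.** 1. With the stimulator attached, ask the surgical-site NRS again immediately before Stimulator A is switched on, and define that reading as the baseline for the primary end point. Leave the limb undisturbed between sensory testing and this reading, or do sensory testing before both pain readings. Otherwise the new baseline would follow a second round of handling.
2. Keep the earlier score and report the difference between the two as drift without current.
3. For subjects given sham first, also record the NRS immediately before active Stimulator B is switched on, and state which reading their primary change uses.
4. Record whether and when the surgeon's examination was done.

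The cost is one or two extra verbal scores per subject and a few sentences in the plan. The headline change may be slightly smaller. The extra reading removes only drift before switch-on; drift during the 5 minutes of current remains, so it does not replace an active-versus-sham comparison in the Stimulator A period. If the schedule table already contains a switch-on reading, it is enough to name that reading as the primary baseline.

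### Stimulator A is randomized to current or sham, but no stated analysis uses the sham score to estimate the effect of active current

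*Combined protocol and SAP*

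**What the plan says.** **Lead placement (Preoperative lead insertion).** Current is passed through each lead "to ensure accurate placement (a pleasant paresthesia in the distribution of the target nerve"). Every subject is therefore meant to have felt active stimulation before being randomized.

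**Randomization.** Two baseline pain scores are taken in the recovery room on the 0-10 NRS, one at the surgical site and one in the target nerve distribution. Stimulator A is then randomized to current or sham, and Stimulator B is the other unit. The "sham stimulator produces no current". On timing the text says "The end points will be measured per the table below", but that table is not in the text available. The lead may be replaced "if a lead fails to provide paresthesias within the target nerve distribution with either Stimulator A or B (adjustment of stimulator settings allowed"). The section adds: "Operating and recovery room pharmacologic analgesic requirements will be recorded".

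**Carry-over paragraph (after Randomization).** "For subjects randomized to active current from Stimulator A, the data collected for Stimulator B placebo treatment may be lowered", and so "this data will not be compared with the baseline or Stimulator A outcome measures". The same paragraph keeps these scores as a possible means of detecting and measuring carry-over, without giving a method.

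**Sample Size Estimation and Statistical Analysis Plan.** The study is a feasibility study whose data are to help design and power later controlled trials. Its primary end point is "the difference between the baseline pain score and pain score 5 minutes after the active (non-sham) electrical stimulator is first turned on". No other effect is defined.

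**The concern.** The trial randomizes a sham control, and the plan then estimates the effect of current without it. A change from baseline contains whatever else moves pain over the same minutes: recovery with time, analgesics given in the recovery room, and the expectation of relief. The two arms also differ in what the change spans. In active-first subjects it is taken on Stimulator A. In sham-first subjects it is taken on Stimulator B, after the whole sham period, when a subject who recognized the sham may be expecting current.

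If a later trial compares active with sham, the quantity it needs is active minus sham, and this plan defines no estimate of that. Any part of the baseline change that also occurs on sham would count as treatment effect if the change were used for sizing. In addition, several sham contrasts are possible. With none named in advance, the choice among them could be made after the data are seen.

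**Working it through.** **1. The plan's own figure.** 40 + 10 = 50, as stated. The 40 is a convenience sample with no alpha, power, effect size or SD, so there is no calculation to reproduce and no figure is contradicted.

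**2. Which sham contrasts remain open.** The carry-over paragraph bars only the Stimulator B sham data of active-first subjects, and only against baseline or Stimulator A.

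| Contrast | Barred? | Between randomized arms at the same point? | Exposed to carry-over from recovery-room stimulation? |
|---|---|---|---|
| Active-A v sham-A | No | Yes | No |
| Active-B v sham-B | No | Yes | Yes (sham-B follows current) |
| Sham-A v baseline (sham-first) | No | No | No |
| Sham-A v active-B (sham-first) | No | No | No, but confounded with time |
| Sham-B v baseline or active-A (active-first) | Yes | No | Yes |

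Active-A v sham-A is the one contrast that is both randomized at the same point and free of that carry-over. Current passed at lead placement precedes randomization and applies to both arms.

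**3. Precision of active-A minus sham-A.** Assumptions, none in the documents: 1:1 allocation, NRS SD 2 to 3, baseline correlation r = 0.5.

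- Unadjusted 95% half-width = t(2n-2) × SD × √(2/n). For n = 20 and SD 2: 2.024 × 2 × 0.3162 = 1.28.
- Adjusted 95% half-width = t(2n-3) × SD × √(1 - r²) × √(2/n). For n = 20 and SD 2: 2.026 × 2 × 0.8660 × 0.3162 = 1.11.

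| Per arm | SD 2 | SD 2.5 | SD 3 |
|---|---|---|---|
| 20, unadjusted | 1.28 | 1.60 | 1.92 |
| 20, adjusted | 1.11 | 1.39 | 1.66 |
| 25, unadjusted | 1.14 | 1.42 | 1.71 |
| 25, adjusted | 0.99 | 1.23 | 1.48 |

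For comparison, the primary change in 40 subjects has half-width t(39) × SD/√40, or 0.64 to 0.96 for an SD of change of 2 to 3. It is tighter, but it estimates a different quantity.

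**4. Illustration of the stake.** Let s be the share of the baseline change that also occurs on sham (assumed), and k = 1 - s. A two-arm trial sized on the full change for 90% power at two-sided 5% has power Φ(k × (1.960 + 1.2816) - 1.960) for the active-sham difference. The SD cancels. The sample-size multiplier is 1/k².

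| s | Power | Multiplier |
|---|---|---|
| 25% | Φ(2.431 - 1.960) = 0.681 | 1.78 |
| 33% | Φ(2.161 - 1.960) = 0.580 | 2.25 |
| 50% | Φ(1.621 - 1.960) = 0.367 | 4.00 |

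A noncentral-t check (assumed change 3 points, SD 2.5) plans 16 per arm. Its actual power is 0.693, 0.591 or 0.376, and 27, 34 or 60 per arm would be needed.

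**The case against.** The study calls itself a feasibility study and not definitive, and it does not say that the primary change will size anything. The shares of 25% to 50% are assumed, and the resulting power loss would follow in any study with those shares. The loss also requires that a later trial compares with sham and that its designers enter a baseline change as the between-arm effect. The proposed contrast is wide: an observed difference smaller than its half-width has an interval that includes zero. All of this stands. It is why the estimate should carry no test, and why this plan should not dictate which effect size a later trial uses. It does not supply the missing active-sham estimate.

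Four stronger readings are tempting, and the documents do not support them:

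- *The sham scores are not used at all.* The carry-over paragraph gives those of active-first subjects an exploratory use.
- *Subjects are in effect unblinded.* Recognition is an inference from a zero-current sham and the paresthesia felt at placement, which may be up to 2 weeks before surgery. What subjects are told about sensation is not in the text available.
- *The 5-minute sham score, a paresthesia record or a treatment guess is not collected.* The end-point table is not shown, so nothing follows from its absence.
- *The power figures apply equally to an expectation component in the Stimulator A difference.* They would only if the later trial's sham removed that expectation. With the same no-current sham, the expectation would recur there.

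**Conclusion.** The point holds as an inexpensive improvement, not as an error that invalidates the study. The one effect defined is an uncontrolled within-subject change, and no stated analysis uses the sham score to estimate the effect of current, although the arms needed are already randomized. This does not depend on whether the sham is recognized: with perfect masking the primary would still be uncontrolled. Recognition bears only on how the added contrast should be labelled.

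The contrast would be an estimate with a wide interval, about ±1.28 to ±1.92 points unadjusted or ±1.11 to ±1.66 adjusted, given 20 per arm, SD 2 to 3 and r = 0.5. The 68%, 58% and 37% power figures only illustrate assumed shares and do not predict the result for this trial.

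**What to change.** Leave the primary end point as it is and add to the Sample Size Estimation and Statistical Analysis Plan:

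1. One pre-specified secondary estimate: active minus sham pain score 5 minutes into Stimulator A, between arms as randomized, adjusted for the same score at baseline, given as a mean difference with 95% CI and no significance test.
2. Which NRS score is meant, surgical site or target nerve distribution. It should be the same for the primary and for this estimate; the section now says only that it is a pain score.
3. A statement that the primary is an uncontrolled change, with the two estimates reported side by side.
4. A statement that, because the sham gives no current and is plausibly recognizable, the active-sham difference may still include expectation.

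The cost is a few sentences, with no change to any study procedure. No new data are needed if the 5-minute score is taken on both units. The Randomization text describes one Stimulator A schedule whichever unit is attached, and the primary already needs a 5-minute score there in active-first subjects. Confirm this in the end-point table. Two limits remain: the interval will be wide, and the last statement discloses expectation without removing it.

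### The primary end point is an uncontrolled before-after change, and no active-versus-sham analysis is specified although Stimulator A is randomized to current or sham

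*Combined protocol and SAP*

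**What the plan says.** - **Primary end point** (Sample Size Estimation and Statistical Analysis Plan): "the difference between the baseline pain score and pain score 5 minutes after the active (non-sham) electrical stimulator is first turned on". The section describes a feasibility study in a convenience sample of 40 (up to 50), meant to show proof of concept and to inform the design and power of later randomized controlled trials. It names no test, alpha, SD or comparison between groups.
- **Randomization**: for Stimulator A, "subjects will be randomized to one of two treatments", current or sham, by computer-generated list and sealed envelopes. Stimulator B is then the other treatment. The sham is inert: "sham stimulator produces no current".
- **Measurements** (Randomization): baseline includes "a pain score at the surgical site using the Numeric Rating Scale (NRS, 0-10), pain score (NRS) within the target nerve distribution". For the stimulator periods, "The end points will be measured per the table below"; that table is not in the text available to me. On analgesics, "Operating and recovery room pharmacologic analgesic requirements will be recorded", with nothing on how they enter the analysis.
- **Carry-over paragraph** (after Randomization): in subjects given current first, the Stimulator B sham data will not be compared with baseline or Stimulator A. No other comparison is excluded, and none is specified.

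**The concern.** A change from baseline in treated subjects estimates the device effect only if pain would otherwise have stayed the same. In a recovery room that is hard to assume. Placebo response, the natural course of pain and analgesics given at the time can each move the score, and the error can go either way: a placebo response can pass for benefit, and rising pain can hide one.

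The pooled change also combines two intervals. For active-first subjects it runs from baseline to 5 minutes into Stimulator A. For sham-first subjects active current first arrives with Stimulator B, so their change also covers the sham period and the exchange of units. A second baseline before Stimulator B cannot be ruled out without the table, but the statistical section mentions none.

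What is at stake is the study's stated purpose. A later controlled trial is sized on the active-minus-sham difference and its variability, and the only effect measure planned here supplies neither.

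**Working it through.** The plan gives no power calculation, so it has no figure of its own to reproduce. Its sample size of 40 is used below. Everything else is assumed: two-sided alpha 0.05, t-based tests, 20 subjects per sequence, and NRS SD and baseline correlation r as shown.

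**1. Before-after test with no device effect.** SE = SD of change / √40, df = 39, noncentrality = non-specific fall / SE. At SD 2.5, SE = 2.5/6.325 = 0.395; a 1-point fall gives 1/0.395 = 2.53 and rejection 0.694.

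| Non-specific fall (points) | SD 2 | SD 2.5 | SD 3 |
|---|---|---|---|
| 0.25 | 0.120 | 0.095 | 0.081 |
| 0.5 | 0.338 | 0.235 | 0.177 |
| 1 | 0.869 | 0.694 | 0.538 |

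A valid test would give 0.050 in every cell.

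**2. Before-after change against the randomized contrast.** Simulation, 40,000 runs, NRS SD 2.5, r = 0.5, no device effect. The contrast is an ANCOVA of the Stimulator A score on arm and baseline. Cells show the rejection rate, with the mean estimate in points.

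| Non-specific fall | Before-after | Stimulator A ANCOVA |
|---|---|---|
| 1 under active, 1 under sham | 0.692 (1.00) | 0.050 (0.00) |
| 1 under active, 0.5 under sham | 0.694 (1.00) | 0.109 (0.50) |
| 1 under active, 0 under sham | 0.693 (1.00) | 0.287 (1.00) |
| 0 throughout Stimulator A; 1 by the time of the active score in sham-first subjects | 0.223 (0.50) | 0.050 (0.00) |

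Rows 2 and 3 represent partial and full recognition of the sham. In row 4 half the subjects fall 1 point and half do not, so the pooled change is (0 + 1)/2 = 0.5.

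**3. Precision of the two analyses.** At SD 2.5 and r = 0.5:
- ANCOVA: residual SD = 2.5 × √(1 − 0.25) = 2.165; SE = 2.165 × √(2/20) = 0.685; df = 37; half-width = 2.026 × 0.685 = 1.39.
- Before-after: SD of change = 2.5 × √(2 × (1 − 0.5)) = 2.5; SE = 0.395; half-width = 2.023 × 0.395 = 0.80.

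| ANCOVA versus before-after | r = 0.3 | r = 0.5 | r = 0.7 |
|---|---|---|---|
| 95% half-width (points) | 1.53 vs 0.95 | 1.39 vs 0.80 | 1.14 vs 0.62 |
| Power, true 1-point benefit | 0.253 vs 0.550 | 0.296 vs 0.694 | 0.407 vs 0.890 |
| Detectable with 80% power (points) | 2.17 vs 1.34 | 1.97 vs 1.14 | 1.62 vs 0.88 |

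For a true 2-point benefit at r = 0.5, power is 0.812 versus 0.999. The before-after power figures hold only if there is no non-specific change. With 25 per arm at r = 0.5, the ANCOVA half-width is 1.23 and power is 0.359 at 1 point and 0.892 at 2 points. A 15/25 split gives 1.43, 0.281 and 0.787.

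**The case against.** **It is a feasibility study.** The plan calls itself non-definitive and commits to no test or efficacy decision, so the rejection rates describe a test it never names. This is fair, and it limits the weight of those rates. The bias in the estimate needs no test, however, and the estimate is what later trials would be designed on.

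**The sham may be recognised.** This is the strongest point. Subjects feel paresthesia when the lead is placed, and the sham delivers nothing. If every subject recognises it and shows none of a 1-point placebo response, the randomized contrast carries the same 1.0-point bias; its 29% rejection rate is below 69% only because it is less precise. That limit stands. Randomization would still balance drift and analgesic use, and any placebo response common to both arms cancels.

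**Drift may be small.** Five minutes is short for active-first subjects, although the gap from baseline to switch-on is not stated. The sham-first interval is longer by an amount the text does not give, so the 22% scenario is an illustration and not a prediction.

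**Precision is lost.** With about 30% power for a 1-point benefit, a real effect could be missed. That is a reason to report an interval rather than a verdict, and it makes a key secondary analysis an acceptable alternative to a new primary.

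**The comparison may be intended.** Excluding one comparison suggests that others were planned, and the missing table could contain a 5-minute sham score. But that table is introduced as a measurement schedule; neither point puts a sham term into the primary end point or states an analysis.

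**Conclusion.** The concern holds and should be fixed. The only pre-specified effect measure omits the randomized control that the design already provides, and it pools two different intervals. Followed exactly, the plan gives an estimate biased by the full amount of any non-specific change common to all subjects. With SD 2 to 3 and no device effect, a 0.5-point fall would be declared an effect in 18–34% of trials and a 1-point fall in 54–87%.

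The reading of the text is firm. The sizes are illustrations that depend on the assumed SD, correlation, test, alpha and allocation. How far the randomized contrast removes placebo response depends on sham recognition, which the documents do not quantify.

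**What to change.** 1. Pre-specify the randomized Stimulator A comparison, active versus sham, of pain 5 minutes after switch-on, by ANCOVA on baseline pain, reported as a difference with 95% CI. Make it the primary analysis, or at least the key secondary on which proof-of-concept statements and later power calculations rest.
2. Use the same pain score as the primary end point and say which it is, surgical-site or nerve-distribution pain, since both are measured.
3. Report the before-after change descriptively, separately for active-first and sham-first subjects.
4. State that the contrast is protected from placebo response only as far as the sham is not recognised. Asking subjects to guess their treatment after the Stimulator A score would allow this to be reported.

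**Cost.** A wording change if Stimulator A sham is already scored at 5 minutes; otherwise one added pain score, plus one question if the guess is recorded. The statistical price is the wider interval and lower power shown in the working. No subjects or procedures are added.
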